5.4 Management of Clinical Supplies

5.4.1 Study Drug Packaging and Storage

Estriol vaginal gel and matching placebo will be prepared in aluminum tubes (with internal lacquer) closed with a polyethylene screw cap, containing 10 g of drug product, packaged and shipped by [REDACTED] to the designated packaging/labeling vendor ([REDACTED]). The designated packaging/labeling vendor ([REDACTED]) will then ship the experimental product to the study sites. The investigational product is packaged as a kit containing a tube of vaginal gel and ten 1-g capacity single-use vaginal applicators.

The studies of stability with the investigational product packaged in 10-g tube indicate that the product should be stored under conditions not to exceed +25°C.

Packaging and labelling of the medicinal products will be performed in accordance with GMP and national regulatory requirements.

Each study participant will be provided with an adequate number of 10-g tubes and 1-g capacity vaginal applicators to fulfill the dosing regimen requirements. Study drug provided to each subject at the Baseline Visit will consist of three kits, each containing one 10-g tube and 10 applicators (for 21 expected applications). At the Week 3 Visit, each subject will receive two kits of the study drug/applicators (for 10 expected applications), and at the Week 8 Visit, two additional kits of study drug/applicators (for 8 expected applications) will be provided.

The Principal investigator or sub-investigator must explain to the subject how to administer the vaginal gel. The first application should be performed at site at baseline visit by the investigator or by the subject in the presence of the investigator. Subjects will be instructed to administer the rest of the treatment applications at bedtime to allow for maximum retention of the gel.

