3. STUDY DESIGN

This study is a double-blind, randomized, dose-ranging, placebo-controlled multicenter study with four parallel groups. Approximately 25 sites in five European countries (Czech Republic, Hungary, Italy, Spain and Sweden) will be included in the study. The study setting will include academic hospitals and gynecological clinics. The study population is postmenopausal women who report moderate to severe vaginal dryness as their most bothersome symptom in addition to other symptoms and/or signs of postmenopausal vulvovaginal atrophy.

After providing informed consent, potential subjects will be evaluated during the screening period (maximum 30 days) to determine if they are eligible to participate in the study. A screening identification number will be assigned to each eligible subject according to their order of arrival into the study at the Screening visit. Subjects who meet all of the inclusion criteria and none of the exclusion criteria (see Sections 4.1.1 and 4.1.2 of the study protocol) will be randomized into the study at the Baseline visit. A total of 280 subjects will be enrolled and randomly allocated to one of the four treatment groups (0.005%, 0.002%, or 0.0008% estriol vaginal gel or placebo vaginal gel); the allocation to treatment group will be 1:1:1:1. A blocked randomization across the entire study (i.e. all sites as a whole) will be used. Subjects will be assigned a randomization code according to their order of arrival into the study at the Baseline Visit. Initial treatment consists of daily vaginal administration of 1 gram of randomly-assigned estriol gel or placebo gel using the supplied applicator. Placebo gel will be identical in appearance, texture and odor to the estriol vaginal gel products. After 21 days of daily administration, treatment will continue with twice-weekly administration up to Week 12 (i.e., Mondays and Thursdays).

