Extent of exposure (days) will be summarized using summary statistics for continuous variables (number of subjects [n], mean, standard deviation [SD], median, quartiles, minimum and maximum).

Compliance

The first administration of study treatment will be conducted at the Baseline visit, either by the investigator or by the subject in the presence of the investigator. Study treatment will then be administered once daily, at bedtime, until the Week 3 visit, and twice weekly after the Week 3

visit until the Week 12 visit. Therefore, the expected number of total applications for each subject will be calculated in 3 stages, as follows:

(1) The expected number of applications from Baseline to Week 3 will be calculated as:

$$\text{Expected Applications from Baseline to Week 3} = \text{Date of Week 3 visit} - \text{Date of Baseline visit}$$

This calculation assumes no application of study treatment on the day of the Week 3 visit, based on the bedtime dosing regimen.

If a subject discontinues prior to the Week 3 visit, the date of last administration of study treatment from the 'End of Study' page of the eCRF will be used instead, and the expected number of applications will be calculated as:

$$\text{Expected Applications from Baseline to Week 3} = \text{Date of Last Administration of Study Treatment}^{[C]} - \text{Date of Baseline Visit}$$

(2) The expected number of applications from Week 3 to Week 12 will be calculated using the algorithm below.

(i) The duration, in weeks, between the Week 3 visit and the Week 12 visit will be calculated as:

$$\text{Weeks from Week 3 to Week 12} = (\text{Date of Week 12 Visit} - \text{Date of Week 3 Visit}) / 7$$

(ii) If (i) is an integer, i.e. a number of whole weeks, the expected number of applications from Week 3 to Week 12 will be calculated as:

$$\text{Expected Applications from Week 3 to Week 12} = (\text{Weeks from Week 3 to Week 12}) \times 2$$

(iii) If (i) is not an integer and the decimal part of (i) is < 0.5 , the expected number of applications from Week 3 to Week 12 will be calculated as:

$$\text{Expected Applications from Week 3 to Week 12} = [(\text{Weeks from Week 3 to Week 12}) \times 2] + 1$$

(iv) If (i) is not an integer and the decimal part of (i) is ≥ 0.5 , the expected number of applications from Week 3 to Week 12 will be calculated as:

$$\text{Expected Applications from Week 3 to Week 12} = [(\text{Weeks from Week 3 to Week 12}) \times 2] + 2$$

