(3) The expected number of total applications from Baseline to Week 12 will be calculated as:

$$\text{Expected Applications from Baseline to Week 12} = \text{Expected Applications from Baseline to Week 3} + \text{Expected Applications from Week 3 to Week 12}$$

The actual number of total applications for each subject will be calculated as the total of all applicators used from all kits according to the 'Study Drug Administration and Compliance – Cumulative' page^[B] of the eCRF.

The percentage compliance for each subject will then be calculated as:

$$\frac{\text{Actual Number of Total Applications}}{\text{Expected Applications from Baseline to Week 12}} \times 100$$

Treatment compliance (%) will be summarized using summary statistics for continuous variables (number of subjects [n], mean, standard deviation [SD], median, quartiles, minimum and maximum). The number and percentage of subjects with compliance by category (< 80%, 80% - 120%, >120%) will also be presented. The denominator of percentage will be the number of subjects who received study treatment and have a calculated compliance value available.

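### The SAP's rule for expected applications from Week 3 to Week 12 counts a part week twice, so compliance is slightly understated whenever the interval is not a whole number of weeks

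*SAP*

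**What the plan says.** SAP section 6.2.4 computes expected applications in three stages.

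- Stage 1, Baseline to Week 3: one application per day, taken as the difference between the two visit dates.
- Stage 2, Week 3 to Week 12: step (i) divides the difference in visit dates by 7. Rule (ii) covers whole weeks and gives twice the number of weeks. Rules (iii) and (iv) cover the rest. Each opens "If (i) is not an integer and the decimal part of (i) is" and then gives its condition: below 0.5 for (iii), 0.5 or more for (iv). Both double the quantity from step (i); (iii) then adds 1 and (iv) adds 2.
- Stage 3 adds the two counts. Percentage compliance is applicators used divided by this total.

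The same section then plans a breakdown: "The number and percentage of subjects with compliance by category", with cuts at 80% and 120%. The outputs are Table 14.1.4 and Listing 16.2.5.2.

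On the regimen, SAP section 3 says "treatment will continue with twice-weekly administration up to Week 12 (i.e., Mondays and Thursdays". Protocol section 5.4.1 gives the nominal supply after Week 3 as "for 10 expected applications" up to Week 8, then 8 more up to Week 12. SAP sections 4.1.3 and 4.1.4 repeat both figures.

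**The concern.** Rules (iii) and (iv) test the decimal part of the step (i) result, so that result has not been truncated. Doubling it already gives credit for the part week, and the added 1 or 2 gives credit again. Nothing else in either document says that only whole weeks are to be doubled.

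At stake is the denominator of a planned Safety-population summary. The error runs one way: expected applications are too high, so compliance is too low, and women near the 80% cut may be placed on the wrong side of it. There is also a programming risk. One programmer may code the text as written and another may silently truncate, and their results would then disagree.

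**Working it through.** **Inputs.** The Week 3 visit window is ±3 days and the Week 12 window ±5 days (Table 1 of both documents). Nominal applications are 21 to Week 3, 10 to Week 8 and 8 to Week 12 (Protocol 5.4.1). The rules are those of SAP 6.2.4.

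**The plan's own figure.** The nominal interval is 63 days: 63/7 = 9 whole weeks, and rule (ii) gives 2 × 9 = 18 = 10 + 8. With the 21 daily applications the total is 39. The rule is right on the nominal schedule.

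**Part-week intervals.** With w = days/7, the text gives 2w + 1 (decimal part < 0.5) or 2w + 2 (decimal part ≥ 0.5). The whole-week version is 2 × floor(w) plus the same 0, 1 or 2. The last column is the largest number of Monday and Thursday nights that the interval can hold, over all seven starting weekdays.

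| Days | w | As written | Whole-week version | Excess | Most Mon/Thu nights |
|---|---|---|---|---|---|
| 55 | 7.857 | 17.71 | 16 | 1.71 | 16 |
| 62 | 8.857 | 19.71 | 18 | 1.71 | 18 |
| 63 | 9.000 | 18.00 | 18 | 0 | 18 |
| 64 | 9.143 | 19.29 | 19 | 0.29 | 19 |
| 66 | 9.429 | 19.86 | 19 | 0.86 | 19 |
| 67 | 9.571 | 21.14 | 20 | 1.14 | 20 |
| 69 | 9.857 | 21.71 | 20 | 1.71 | 20 |
| 70 | 10.000 | 20.00 | 20 | 0 | 20 |

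The count as written falls by 1.71 from 62 to 63 days and again from 69 to 70 days, although a longer interval cannot call for fewer applications. From 55 to 71 days it exceeds the Monday/Thursday maximum at every part-week interval, while the whole-week version equals that maximum at every interval. Measured against simple proportion (2w), the excess is exactly 1 or 2.

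**How many visit patterns are affected.** Let a be the Week 3 offset (−3 to +3) and b the Week 12 offset (−5 to +5). This gives 7 × 11 = 77 combinations, with interval 63 + b − a and 21 + a applications before Week 3. Whole-week intervals arise in 11 combinations: 2 at 56 days, 7 at 63 and 2 at 70. The other 66 are affected, and 66/77 = 86%. Over all 77, equally weighted, the mean excess is 0.86.

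**Effect on a fully compliant woman.** The lowest value comes from a = −3, b = −4, which gives 18 early applications and a 62-day interval. She uses 18 + 18 = 36 applicators against 18 + 19.71 = 37.71 expected, and 36/37.71 = 95.5%. The equally weighted mean over the 77 combinations is 97.9%.

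**Effect at the 80% cut.** In that same pattern, 30 applicators are 30/36 = 83.3% on the whole-week count but 30/37.71 = 79.5% as written. No higher true compliance changes category in any of the 77 combinations. Because applicators are whole numbers, 25 combinations allow no count to cross the cut, 45 allow one and 7 allow two.

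**The case against.** The strongest reply is that little depends on this. Compliance is summarised descriptively, enters no efficacy model, and is not among the programmed per-protocol exclusions in SAP 6.2.2. All four arms use the same formula, and nothing points to a difference between arms. All of this stands, and it is why the point is minor.

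A reader might infer that the denominator is wrong for most subjects. The documents do not support that. The 86% is a share of visit-day combinations, and it becomes a share of subjects only if those combinations are equally likely. Protocol 6.1.3 and 6.1.5 ask sites to schedule close to the ideal date, and a 63-day interval gives the right count.

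A reader might also infer that the per-protocol population changes. SAP 6.2.2 does allow exclusion for product non-compliance, but those deviations are classified under a separate deviation plan that is not among the documents. No link from this percentage to an exclusion can be shown. Nor is an adherent woman mislabelled: at 95.5% or more she stays in the 80% to 120% category.

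A further objection is that the whole-week version is itself an inference. It is a ceiling: against simple proportion it is high by 0.14 to 0.86 applications in part-week intervals. It also leans on the Monday/Thursday pattern, which the protocol offers only as a preferred example in the treatment section. If the two weekly applications were one day apart, the count as written would not exceed the possible maximum at 58, 59, 65 or 66 days; two days apart, the same holds at 59 and 66. This stands as a caution about the choice of benchmark. It does not rescue the text, which exceeds simple proportion by 1 or 2 in every part-week interval and still falls as the interval lengthens.

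**Conclusion.** The rule is wrong as written for every Week 3 to Week 12 interval that is not a whole number of weeks. Against the whole-week version, expected applications are too high by 0.29 to 1.71 for in-window visits. Reported compliance for a fully compliant woman is then between 95.5% and just under 100%. Some women with true compliance of 80.0% to 83.3% are shown as <80%.

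These figures rest on three assumptions: visits within the windows, 21 nominal applications before Week 3 adjusted for the actual Week 3 date, and the whole-week count as the benchmark. Out-of-window and early-termination visits are not covered. The number of subjects affected cannot be stated without the actual distribution of visit dates.

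The consequence is limited to Table 14.1.4 and Listing 16.2.5.2. Severity: minor.

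**What to change.** In SAP 6.2.4, rules (ii) to (iv), replace the number of weeks by its integer part before doubling: expected = 2 × floor(weeks) + 0 for whole weeks, + 1 if the decimal part is below 0.5, + 2 if it is 0.5 or more. State that this is the largest count compatible with a Monday/Thursday pattern, so that the choice over simple proportion is explicit.

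The cost is one function in the derivation and one sentence in the SAP. No new data are needed, no dosing instruction changes, and the nominal 18 (39 in total) is unchanged.

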6.2.5 Prior and Concomitant Medications and Therapies

Prior and Concomitant Medications

The minimum requirement is that the drug name and the dates of administration are to be recorded in the eCRF. This will include all prescription drugs, herbal products, and over-the-counter (OTC) medications from 28 days prior to the start of study treatment and up to 30 days (\pm 5 days) following the last dose of investigational product; the reason for the drug administration must be recorded in the eCRF. Any changes in concomitant medications also will be recorded in the subject's eCRF.

All prior and concomitant medications will be classified using the World Health Organization Drug Dictionary Enhanced (WHO DDE). The WHO DDE Version June 2016 will be used, with one update during the study as per the Data Management Plan. The Anatomical Therapeutic Chemical (ATC) Classification Level 2 and Preferred Term will be used to list and summarize the data.

Prior Medications are defined as the medications (recorded on the Prior and Concomitant Medications page of the eCRF) that started and stopped before the date of first administration of study treatment captured on the 'Study Drug Administration – Baseline' page of the eCRF. Only medications where the stop date is prior to the date of first administration of study treatment exclusive will be considered *prior medications*. If the stop date is unknown or incomplete and the medications cannot definitely be considered as stopped prior to Baseline then the medications will be considered as *concomitant medications*. Medications for subjects who were not treated with study treatment will be considered as *prior medications*.

Concomitant Medications are defined as the medications (recorded on the Prior and Concomitant Medications page of the eCRF) that either started before the date of first administration of study treatment and continued into the study, or medications that started during the study.

The number and percentage of subjects reporting the use of any prior medications, and the number of reported prior medications by ATC level 2, preferred term, treatment and overall will be summarized for the Safety population. This table will be repeated for concomitant medications.

Other Concomitant Diagnostic or Therapeutic Procedures

All other concomitant diagnostic or therapeutic procedure terms (recorded on the Other Concomitant Diagnostic or Therapeutic Procedures page of the eCRF) will be classified using the Medical Dictionary for Regulatory Activities (MedDRA) coding dictionary. MedDRA Version 19.0 will be used, with one update during the study as per the Data Management Plan.

Other concomitant diagnostic and therapeutic procedures will be summarized by system organ class (SOC), preferred term, treatment and overall for the Safety population. The number and percentage of subjects having each coded term, and the number of events under each term will be presented. If a subject reports multiple diagnostic or therapeutic events with the same preferred term (i.e. with distinct start and stop dates), these shall be summarized once within the count of subjects, but each event will be counted within the count of events.

6.2.6 Medical History

All medical history terms will be classified using the MedDRA coding dictionary. MedDRA Version 19.0 will be used, with one update during the study as per the Data Management Plan.

Medical history will be summarized by SOC, preferred term, treatment and overall for the Safety population. The number and percentage of subjects having each medical history term, and the number of events under each term will be presented. If a subject reports multiple medical history events with the same preferred term (i.e. with distinct start and stop dates), these shall be summarized once within the count of subjects, but each event will be counted within the count of events.

6.3 Efficacy Analysis

6.3.1 Primary Efficacy Analysis

The four co-primary efficacy variables in this study are:

- Change from Baseline to Week 12 in the severity of vaginal dryness
- Change from Baseline to Week 12 in vaginal pH
- Change from Baseline to Week 12 in the proportion of superficial cells of the vaginal epithelium

- Change from Baseline to Week 12 in the proportion of parabasal cells of the vaginal epithelium

The planned analyses of each of these four endpoints and the gatekeeping procedure to be employed for obtaining conclusions are described in **Sections 6.3.1.1 to 6.3.1.5** below.

The primary analyses will be performed using the ITT population using LOCF methodology, and confirmatory analyses will be performed using the PP population (using observed data only, since having Week 12 data available is a requirement for inclusion in the PP population). It should be noted that, since the statistical tests are one-sided, only one limit of each confidence interval presented (the limit in the direction where Estriol vaginal gel is favorable for each specific endpoint) is of particular interest for analysis. Each statistical test will examine the null hypothesis that Estriol vaginal gel is no different to Placebo against the alternative hypothesis that Estriol vaginal gel is superior to Placebo.

No adjustment for multiplicity will be made, since statistical significance in all 4 co-primary endpoints is required to declare efficacy. The minimal effective dose will be considered to be the lowest dose at which a significant difference is seen (in favor of Estriol) when compared with Placebo.

6.3.1.1 Change from Baseline to Week 12 in Severity of Vaginal Dryness

Vaginal dryness is one of the five symptoms of vulvovaginal atrophy, and is self-assessed by the subject at the Screening, Week 3 and Week 12 / Early Termination visits.

Each symptom will be scored by the subject using a numeric scale from 0 to 3, as follows:

0	Absent:	The symptom is not present
1	Mild:	The symptom is of mild intensity
2	Moderate:	The symptom is of moderate intensity
3	Severe:	The symptom is severe in intensity

The number and percentage of subjects with each severity of vaginal dryness at each visit will be summarized by treatment in a general summary table of symptoms of vulvovaginal atrophy.

Given that the Inclusion Criteria for the study require the subject to have moderate (score of 2) or severe (score of 3) vaginal dryness at Baseline (Screening), the change from Baseline to Week 12 may take the possible values ranging from -3 (Severe at Screening; Absent at Week 12) to 1 (Moderate at Screening; Severe at Week 12).

The number and percentage of subjects with each ordinal change from Baseline to Week 12 value (-3, -2, -1, 0 and 1) will be summarized by treatment group.

The change from Baseline to Week 12 in vaginal dryness will be analyzed using a Wilcoxon Rank Sum test, controlled for country, to obtain the one-sided p-values for each treatment

comparison (0.005% Estriol versus placebo, 0.002% Estriol versus placebo and 0.0008% Estriol versus placebo) by means of the FREQ procedure in SAS with the SCORES = RANK option. The Hodges-Lehmann estimate of median difference between treatment groups will also be presented for each of the three treatment comparisons above, along with 95% CIs, by means of the NPAR1WAY procedure in SAS. Hodges-Lehmann estimates will be presented without the adjustment for country, since SAS does not currently produce Hodges-Lehmann estimates when covariates are included. Missing values at Week 12 will be estimated using LOCF methodology for the ITT population analysis only. Only post-Baseline values will be carried forward.

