7.8.1 Analysis of Primary Efficacy Endpoints

The changes from baseline to Week 12 in vaginal dryness will be analyzed using a Wilcoxon Rank Sum test, controlled for country, to obtain the p-values. The Hodges-Lehmann estimate of median difference between treatment groups (0.005% versus placebo, 0.002% versus placebo and 0.0008% versus placebo) will also be presented with 95% confidence intervals. It should be noted that, since the statistical tests are one-sided, only one limit of each confidence interval is of particular interest for analysis. Details of statistics to be presented will be described in the Statistical Analysis Plan. Missing values at Week 12 will be estimated using the last observation carried forward (LOCF). Only post-Baseline values will be carried forward.

The changes from baseline to Week 12 in vaginal pH, and the changes in proportions of parabasal and superficial cells will be analyzed using a parametric ANCOVA model. The model will include fixed effects of treatment and country, and the baseline value will be used as a covariate. The adjusted (least-square) mean change from baseline to Week 12 will be presented for each treatment, along with the corresponding standard error. The difference in adjusted means between treatment groups (0.005% versus placebo, 0.002% versus placebo and 0.0008% versus placebo) will also be presented with 95% confidence intervals and p-values. It should be noted that, since the statistical tests are one-sided, only one limit of each confidence interval is of particular interest for analysis. Model assumptions will be examined and, if required, a Wilcoxon Rank Sum test as described for vaginal dryness will be used. Missing values will be estimated using LOCF. Only post-Baseline values will be carried forward.

No adjustment for multiplicity will be made, since statistical significance in all four co-primary endpoints is required to declare efficacy.

The robustness of the LOCF approach for missing data will be addressed by completing a sensitivity analysis. This will be an observed case analysis and will use no imputation methods in order to assess the robustness of the results.

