6.1.4 Determination of Sample Size

A total of 280 female subjects will be enrolled in the study.

The estimates of treatment differences and variability were gained from the results of Study ITFE-2026-C2.

A sample size of 57 in each group will have 90% power to detect a treatment difference for change in severity of vaginal dryness, assuming five categories with proportions in each treatment group as shown in **Table 2** below, using a Wilcoxon rank sum test with a 0.025 one-sided significance level.

Table 2: Assumed Proportions for Wilcoxon Rank Sum Test of Vaginal Dryness

Change in Vaginal Dryness Severity	Proportion in Estriol Vaginal Gel Group	Proportion in Placebo Group
-3	0.189	0.118
-2	0.423	0.196
-1	0.270	0.353
0	0.118	0.333

Change in Vaginal Dryness Severity	Proportion in Estriol Vaginal Gel Group	Proportion in Placebo Group
1	0	0

A sample size of 48 in each group will have 90% power to detect a treatment difference of -0.89 for change in vaginal pH, assuming a common standard deviation of 1.33 using a two-group t-test with a 0.025 one-sided significance level.

A sample size of 24 in each group will have 90% power to detect a treatment difference of 21 for change in proportion of superficial cells, assuming a standard deviation of 26.3 for 0.005% estriol vaginal gel and 14.8 for placebo vaginal gel, using a two-group Satterthwaite t-test with a 0.025 one-sided significance level.

A sample size of 9 in each group will have 90% power to detect a treatment difference of -53 for change in proportion of parabasal cells, assuming a standard deviation of 37.9 for 0.005% estriol vaginal gel and 19.6 for placebo vaginal gel, using a two-group Satterthwaite t-test with a 0.025 one sided significance level.

The largest sample size calculated for a single co-primary endpoint has been considered the sample size required for the whole study, thus, 57 subjects per group are estimated. Accounting for an 18% drop-out rate, and rounding numbers, approximately 70 subjects/group have been finally estimated.

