6.3.1.2 Change from Baseline to Week 12 in Severity of Vaginal pH

A vaginal pH determination will be performed at the Screening, Week 3 and Week 12 / Early Termination visits.

The vaginal pH will be summarized using descriptive statistics for continuous variables by treatment and visit. The change from Baseline (Screening) value will also be summarized for all post-Baseline visits.

The mean change in vaginal pH from Baseline to the Week 12 / Early Termination visit will be analyzed using a parametric analysis of covariance (ANCOVA) model. The model will include treatment and country as fixed effects and the Baseline (Screening) pH will be used as a covariate. The adjusted (least-square) mean (LS Mean) change in vaginal pH from Baseline to Week 12 will be presented for each treatment, along with the corresponding SE. The difference in LS Means between treatment groups (0.005% Estriol versus Placebo, 0.002% Estriol versus Placebo and 0.0008% Estriol versus Placebo) will also be presented with 95% CI and one-sided p-value. The p-values for the model parameters of country and Baseline pH will also be presented. Model assumptions will be examined and, if required, a Wilcoxon Rank Sum test as described for vaginal dryness (Section 6.3.1.1) will be used. Missing values at Week 12 will be estimated using LOCF methodology for the ITT population analysis only. Only post-Baseline values will be carried forward.

6.3.1.3 Change from Baseline to Week 12 in Proportion of Superficial Cells of the Vaginal Epithelium

Vaginal smears will be performed at the Screening, Week 3 and Week 12 / Early Termination visits. Two vaginal smears will be collected per subject at each visit, with one cytological sample sent to the central laboratory [REDACTED] for analysis, and one sample retained at site for backup purposes. The samples sent to [REDACTED] will be evaluated by two different cytopathologists who will be blinded to subject, treatment assignment and to each other's evaluations. The number and percentage of superficial cells will be provided for each pathologist's cytologic evaluation, and the percentages will be converted to proportions for statistical presentation.

The proportion of superficial cells of a given subject and visit to be used for analysis will be derived as the mean result across the two pathologists. The evaluations of both pathologists must be verified by the Clinical Research Associate (CRA) in order to be considered for final analysis.

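### The vaginal dryness co-primary is tested without adjustment for Screening severity, unlike the other three co-primaries; the test is valid, but some precision and protection against chance imbalance are given up

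*SAP*

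**What the plan says.** SAP 6.3.1.1 states that the change in dryness "will be analyzed using a Wilcoxon Rank Sum test, controlled for country, to obtain the one-sided p-values for each treatment" comparison. Protocol 7.8.1 names the same test, with country as the only control.

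The same SAP section notes that entry requires a Screening score of 2 or 3, and concludes that the change "may take the possible values ranging from -3 (Severe at Screening; Absent at Week 12) to 1".

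For pH and the two cell proportions, Protocol 7.8.1 says: "The model will include fixed effects of treatment and country, and the baseline value will be used as a covariate". SAP 6.3.1.2 repeats this for pH ("the Baseline (Screening) pH will be used as a covariate"), and 6.3.1.3 and 6.3.1.4 do the same for the cell proportions.

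Protocol 3.1 and SAP 3 describe randomization blocked over the trial as a whole. Neither mentions stratification by dryness severity.

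SAP 6.1.4 sizes the trial on dryness: "A sample size of 57 in each group will have 90% power to detect a treatment difference for change in severity of vaginal dryness", with the Table 2 distributions of change and "using a Wilcoxon rank sum test with a 0.025 one-sided significance level".

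**The concern.** On the 0 to 3 scale, a woman who enters at 3 can change by -3 to 0 and one who enters at 2 by -2 to +1. The value -3, given to 18.9% of estriol and 11.8% of placebo women in Table 2, can come only from severe women. Baseline is therefore likely to explain part of the variation in change. The planned test leaves that part in the noise, although the score is already collected.

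Dryness needs the largest sample of the four co-primaries (57 per group, against 48, 24 and 9). A dose passes only if all four are significant, and a failure stops the dose sequence. Precision on dryness therefore bears directly on the minimal effective dose. With no stratification by severity, an arm can also receive more severe women by chance, and the unadjusted test has no means of correcting for it.

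The one dryness analysis that uses baseline as a covariate is the sensitivity mixed model in SAP 6.3.1.6. It does not fill the gap, because it assigns ranks inside each treatment group. Ranks taken separately in two arms of 57 both average (57 + 1)/2 = 29.0, which removes the treatment contrast if done as written.

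**Working it through.** **1. The plan's own figure.** Table 2, for changes -3, -2, -1, 0: estriol 0.189, 0.423, 0.270, 0.118; placebo 0.118, 0.196, 0.353, 0.333.

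- P(estriol better) = 0.189×0.882 + 0.423×0.686 + 0.270×0.333 = 0.5468.
- P(tie) = 0.189×0.118 + 0.423×0.196 + 0.270×0.353 + 0.118×0.333 = 0.2398.
- P(better) + ½P(tie) = 0.6667.

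With a tie-corrected null variance and a separate variance under the alternative, power is 90.1% at 56 per group and 90.6% at 57. Using the null variance throughout gives 89.1% at 57, and the tie-corrected Noether formula gives 58.3 per group. The planned 57 reproduces, and 57/(1 - 0.18) = 69.5, rounded to 70.

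**2. Effect of adjustment on power.** The severe share and the split of change by baseline are not in the documents, so both are assumed. Joint tables of baseline by change were fitted to the Table 2 margins, with -3 impossible from a moderate baseline. An association parameter tilts severe women towards more improvement (positive) or less (negative); 0 means no association beyond the impossible -3. Simulated power at 57 per arm, one-sided 0.025, country ignored:

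| Severe share | Association | Wilcoxon on change | Rank ANCOVA |
|---|---|---|---|
| 30% | -0.5 | 90.4% | 93.5% |
| 30% | 0 | 90.8% | 95.2% |
| 30% | 0.5 | 90.1% | 96.7% |
| 30% | 2 | 90.8% | 99.0% |
| 50% | -0.5 | 90.6% | 90.8% |
| 50% | 0 | 89.9% | 92.1% |
| 50% | 0.5 | 90.4% | 94.5% |
| 50% | 2 | 90.7% | 98.9% |
| 70% | -0.5 | 89.7% | 89.6% |
| 70% | 0 | 90.0% | 90.8% |
| 70% | 0.5 | 90.2% | 92.7% |
| 70% | 2 | 90.7% | 98.0% |

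The largest gain is 99.0 - 90.8 = 8.2 points; the smallest is nil. With five countries as strata (assumed shares 30/25/20/15/10%) and 30% to 60% severe, the planned test had 88-90% power and the country-stratified rank ANCOVA 87-95%. That runs from a loss of about 1 point to a gain of about 6. The loss arises because a slope is estimated in each country even when baseline carries little information.

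**3. Average false-positive rate.** With no treatment effect and severity left to chance, the unadjusted test rejected in 2.3-2.5% of simulated trials and the adjusted test in 2.1-2.7%. Both are at the nominal 2.5%.

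**4. False-positive rate given an imbalance.** Fix 60% severe on estriol and 40% on placebo, with no treatment effect. The unadjusted test then rejects in about 3% to 9% of trials, depending on the assumed association; the adjusted test stays near 2.5%. The mirror-image imbalance takes the unadjusted rate below 2.5%.

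**5. How likely that imbalance is.** If 50% are severe, the standard deviation of the difference in severe share at 57 per arm is √(2×0.25/57) = 0.094. A gap of 20 points favouring estriol is 0.20/0.094 = 2.1 standard deviations. The exact binomial probability of a gap at least that large in that direction is about 1.5% (1.1% at 70 per arm). A gap of 10 points or more in either direction occurs in about 30% of two-arm comparisons.

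**The case against.** The strongest reply is that nothing here is wrong. The test is valid, Table 2 is a distribution of raw change, and the trial is sized for the test it plans to run. That stands.

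The 57 is also the number left after dropout. The primary analysis is ITT with last observation carried forward, so the number analysed should lie between 57 and 70. The unadjusted test has about 93% power at 63 and 95% at 70 on the Table 2 effect, so there is less power to gain than the table above suggests. That too stands, with the reservation that carried-forward values may dilute the effect and that the documents give no separate dryness assumption for the two lower doses.

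A reader might infer from step 4 that type I error is inflated. The documents do not support that. The 3-9% is conditional on an uncommon imbalance in one direction, and averaged over randomization the error is about 2.5%.

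A reader might also object that complete relief from moderate dryness (-2) ties with severe dryness reduced to mild (also -2), and conclude that the endpoint is mis-scored. The tie follows from declaring change in severity as the endpoint; both are two-category improvements. Counting complete relief as better would be a different endpoint.

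Finally, SAP 6.3.1.1 plans severity counts by visit and arm, so an imbalance would be visible. Seeing it does not adjust for it.

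**Conclusion.** The point holds as an efficiency improvement. Dryness is the only co-primary without a baseline covariate, the plan gives no reason, and the planned sensitivity analyses do not close the gap. The effect on power at 57 per arm runs from about -1 to +8 points, over assumed severe shares of 30-70% and assumed associations between baseline and change. The documents fix neither, so a material loss in this trial cannot be shown. It would be wrong to call the planned test biased, its error rate inflated or the design underpowered: average one-sided error is about 2.5% and 57 per group reproduces. The case for changing rests on a likely gain in precision on the co-primary that sets the sample size, and on protection against a chance imbalance, at almost no cost.

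**What to change.** Before unblinding, amend SAP 6.3.1.1 and Protocol 7.8.1, and record the change in SAP 6.8:

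- For each dose against placebo, rank the Week 12 change and the Screening dryness score within country, over both arms together. Take residuals of the change ranks on the baseline ranks, and compare them between arms with the country-stratified CMH test in PROC FREQ at one-sided 0.025.
- In any country where all subjects have the same Screening score, use the unadjusted change ranks.
- Keep the present country-controlled Wilcoxon test as a sensitivity analysis.
- Tabulate change by arm separately for moderate and severe baseline.
- State whether the covariate also applies to the analyses that refer back to 6.3.1.1 (secondary symptoms and signs, and the fallback for pH and cell proportions).

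The cost is SAP and protocol wording, a few program lines, and a possible power loss of about 1 point if baseline is nearly unrelated to change. No visit, data collection or sample size changes. The Hodges-Lehmann estimate would remain unadjusted, as the SAP already accepts for country.
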